10.2 Demographics and Patient Disposition

The demographic variables age, sex, race, ethnicity, body weight, height, and body mass index will be summarized and listed. If only a subset of patient's progress from part 1 to part 2 then demographics will be also presented by part. Patient disposition will be summarized and listed.

Disease-specific characteristics and surgical history, including previous cancer treatment will be summarized and listed. Medical history data will be listed.

10.3 Pharmacokinetic Assessment

10.3.1 Pharmacokinetic Analysis

The following PK parameters will be determined where possible from the plasma concentrations of pamiparib and the whole blood and plasma concentrations of total radioactivity using non-compartmental methods performed using Phoenix WinNonlin (Version 8.1 or higher):

Parameter	Definition
AUC _{0-t}	AUC from time 0 to the time of last quantifiable concentration, calculated using the linear trapezoidal rule for increasing concentrations and the logarithmic rule for decreasing concentrations
$AUC_{0-\infty}$	AUC from time zero to infinity
AUC_{0-9}	AUC from time zero to 9 hours postdose
$\mathrm{AUC}_{0\text{-}12}$	AUC from time zero to 12 hours postdose
C_{max}	Maximum observed concentration
t_{max}	Time of C _{max}
λ_{z}	Apparent terminal elimination rate constant
t _{1/2}	Apparent terminal elimination half-life
CL/F	Apparent total plasma clearance (pamiparib only)
V_z/F	Apparent volume of distribution during the terminal elimination phase (pamiparib only)
$AUC_{0\text{-}\infty}Blood/Plasma$	Ratio of AUC _{0-∞} of whole blood total radioactivity relative to
Ratio	AUC _{0-∞} of plasma total radioactivity
AUC _{0-∞} Plasma pamiparib	Ratio of AUC _{0-∞} of plasma pamiparib relative to AUC _{0-∞} of
/ Total Radioactivity Ratio	plasma total radioactivity

Additional PK parameters may be determined where appropriate.

The ratio of AUC total radioactivity in whole blood to AUC total radioactivity in plasma and the ratio of AUC of plasma pamiparib to AUC total radioactivity in plasma will be based on AUC_{0-∞}. Where AUC_{0-∞} cannot be reliably calculated an alternative AUC measure, such as AUC to a common time point or AUC_{0-t}, may be used.

Additionally, blood-to-plasma ratios at each sampling time point will be calculated to determine partitioning of total radioactivity into red blood cells. Plasma pamiparib-to-total radioactivity ratios at each sampling time point will be calculated to determine the fraction of total radioactivity attributed to pamiparib. These ratios will be calculated by the radioanalysis laboratory and reported in the radioanalysis report

The PK analysis will, where possible, be carried out using actual postdose times recorded in the raw data.

Concentrations are used as supplied by the analytical laboratory for PK analysis. The units of concentration and resulting PK parameters, with amount or concentration in the unit, will be presented as they are received from the analytical laboratory.

The C_{max} and t_{max} will be obtained directly from the plasma concentration-time profiles. For multiple peaks, the highest postdose concentration will be reported as C_{max} . In the case that multiple peaks are of equal magnitude, the earliest t_{max} will be reported.

The following excretion parameters will be calculated, whenever possible, based on the urine concentrations of pamiparib using Phoenix WinNonlin (Version 8.1 or higher):

Parameter	Definition
A_{eu}	Amount excreted in urine per sampling interval
Cum A _{eu}	Cumulative amount excreted in urine
CL_R	Renal clearance, where:
	$CL_R = Cum A_{eu} / AUC$
	AUC _{0-∞} may be used, if appropriate (pamiparib only)
$% f_{eu} = f_{eu} = f_{eu}$	Percentage of drug or radioactive dose excreted in urine per sampling interval
Cum %feu	Cumulative percentage of drug or radioactive dose excreted in urine

The amount excreted in urine (A_{eu}) for each collection interval will be calculated as the product of urine concentration and urine sample weight (assuming a specific gravity of 1 g/mL); Cum A_{eu} will be calculated by summing the A_{eu} values for each collection interval over the entire collection period.

The percent of the dose excreted (% f_{eu}) will be calculated for each urine collection interval (i) according to the following formula: % $f_{eu}(i) = [f_{eu}(i) / dose] \times 100$

Cum $\% f_{eu}$ will be calculated by summing the $\% f_{eu}$ values for each collection interval over the entire collection period.

The following PK parameters will be calculated, whenever possible, based on the fecal total radioactivity concentrations:

Parameter	Definition
$\overline{\mathrm{A}_{\mathrm{ef}}}$	Amount excreted in the feces per sampling interval
Cum A _{ef}	Cumulative amount excreted in feces
$% f_{ef}$	Percentage of radioactive dose excreted in feces per sampling interval
Cum %fef	Cumulative percentage of radioactive dose excreted in feces

Excretion parameters for total radioactivity (A_{eu}, Cum A_{eu}, %f_{eu}, Cum %f_{eu}, A_{ef}, Cum A_{ef}, %F_{ef}, and Cum %f_{ef}) will be calculated by the radioanalysis laboratory and reported in the radioanalysis report and therefore not presented within the TFLs.

Statistical Analysis Plan Covance Study: 8381180 Sponsor Reference: BGB-290-106

10.3.2 Criteria for handling concentrations below the limit of quantification in Pharmacokinetic analysis

Concentration values that are below the level of quantification (BLO) will be set to zero, with defined exceptions as follows;

- Any embedded BLQ value (between 2 quantifiable concentrations) and BLQ values following the last quantifiable concentration in a profile will be set to missing for the purposes of PK analysis.
- If there are late positive concentration values following 2 BLQ concentration values in the apparent terminal phase, these values will be evaluated. If these values are considered to be anomalous, they will be set to missing.
- If an entire concentration-time profile is BLO, the profile will be excluded from the PK analysis.
- If a predose concentration is missing, it will be set to zero by default within Phoenix WinNonlin.

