2.2. Endpoints

2.2.1. Primary Endpoints

The following PK outcome endpoints of pamiparib (plasma), and total radioactivity (whole blood and plasma) derived from the concentration-time profiles following a single oral dose of [14C]-pamiparib are as follows:

- AUC from time zero to infinity (AUC_{0- ∞})
- AUC from time zero to the last quantifiable concentration (AUC_{0-t})
- C_{max}
- Time of C_{max} (t_{max})
- $t_{1/2}$
- Apparent total clearance (CL/F)
- Apparent volume of distribution (V_z/F)
- AUC_{0- ∞} of plasma pamiparib relative to AUC_{0- ∞} of plasma total radioactivity (AUC_{0- ∞} Plasma Pamiparib Total Radioactivity Ratio)
- AUC_{0- ∞} of whole blood total radioactivity to AUC_{0- ∞} of plasma total radioactivity (AUC_{0- ∞} Blood/Plasma Ratio).

The primary PK outcome endpoints of pamiparib and total radioactivity derived from urine collections are as follows:

- Amount excreted in urine (A_{eu})
- Cumulative A_{eu}
- Percentage excreted in urine (f_{eu})
- Cumulative f_{eu}
- Renal clearance (CL_R; pamiparib only).

The primary PK outcome endpoints of total radioactivity derived from fecal collections are as follows:

- Amount excreted in feces (A_{ef})
- Cumulative A_{ef}
- Percentage excreted in feces (f_{ef})

12 December 2018 Page 24 of 72

Protocol Amendment Version 3.0 Covance Study: 8381180

• Cumulative f_{ef}.

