9. SAMPLE SIZE AND DATA ANALYSIS

9.1. **Determination of Sample Size**

No formal statistical assessment of sample size has been conducted. The sample size chosen for this study is common in human radiolabeled studies and is considered sufficient to achieve the objectives of the study. Up to approximately 10 patients will be enrolled and studied in order that 4 patients complete Part 1 of the study.

12 December 2018 Page 53 of 72

9.2. **Analysis Populations**

9.2.1. **Pharmacokinetic Population**

The PK population will include all patients who received [14C]-pamiparib and have evaluable PK data. Patients will be excluded from the PK summary statistics and statistical analysis if a patient has an AE of vomiting that occurs at or before 2 times median t_{max} .

CONFIDENTIAL

9.2.2. **Safety Population**

The safety population will include all patients who received [14C]-pamiparib.

9.3. **Pharmacokinetic Analyses**

Plasma and urine PK parameters of pamiparib and whole blood and plasma parameters of total radioactivity will be calculated using standard noncompartmental methods.

Additional noncompartmental PK parameters may be determined where appropriate.

Pharmacokinetic parameters will be summarized using descriptive methodology. No formal statistical analysis will be performed.

Descriptive statistics (mean, median, minimum, maximum, standard deviation, geometric mean, and geometric coefficient of variation) will be calculated for all PK parameters and PK concentration data where applicable.

Specification of PK parameters to be presented in the CSR; procedures for accounting for missing, unused, or spurious data; procedures for reporting deviations from the original statistical plan; and selection of patients to be included in the analyses population(s) will be presented in the CSR and/or the Statistical Analysis Plan as appropriate.

All statistical summary calculations will be performed using SAS® Version 9.4 or greater.

9.4. **Safety Analysis**

All AEs will be listed and summarized using descriptive methodology. No formal statistical analysis will be performed. The incidence of AEs will be presented by severity and by relationship with the study drug as determined by the PI (or designee). Each AE will be coded using the Medical Dictionary for Regulatory Activities.

Patient ECOG performance will be reported for the Safety population and will be listed.

9.5. **Interim Analysis**

No interim analyses are planned for this study.

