10.1 General

Data listings will be provided for the Safety Population. Summary statistics and statistical analyses will be performed for patients included in the relevant analysis populations (Safety/PK).

For continuous data, summary statistics will include the arithmetic mean, arithmetic standard deviation, median, minimum, maximum, and number. For log-normal data (eg, the PK parameters: areas under the concentration-time curve [AUCs] and maximum observed concentration [C_{max}]), the geometric mean and geometric coefficient of variation (CV%) will also be presented. For categorical data, frequency counts and percentages will be presented. Data listings will be provided for all patients up to the point of withdrawal, with any patients excluded from the relevant population highlighted. For the calculation of summary statistics and statistical analysis, unrounded data will be used.

Missing values will not be imputed.

Data analysis will be performed using SAS® Version 9.4 or higher.

Analysis Data Model (ADaM) datasets will be prepared using Clinical Data Interchange Standards Consortium (CDISC) ADaM Version 2.1, and CDISC ADaM Implementation Guide Version 1.1. Pinnacle 21 Community Validator Version 2.2.0 will be utilized to ensure compliance with CDISC standards.

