10.4 Presentation of Pharmacokinetic Data

10.4.1 Presentation of Pharmacokinetic Plasma Drug Concentrations and Total Radioactivity in Whole Blood and Plasma Data

The following rules will be applied if there are values that are BLQ or if there are missing values (eg, no result [NR]) in a concentration data series to be summarized.

- For the calculation of summary statistics, BLQ values will be set to zero.
- If an embedded BLQ value is considered anomalous within the concentration-time profile, this value will be excluded from the summary statistics.
- Where there is NR, these will be set to missing.
- If there are less than three values in the data series, only the min, max and N will be presented. The other summary statistics will be denoted as not calculated (NC). BLQ is considered a value.

• If all the values are BLQ, then the arithmetic mean, arithmetic standard deviation, median, min and max will be presented as zero, and the geometric mean and geometric CV% will be denoted as NC.

• If the value of the arithmetic mean or median is below the LLOQ, these values will be presented as zero and the geometric mean and geometric CV% will be denoted as NC.

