10.4.2 Presentation of Pharmacokinetic Parameters

For the calculation of summary statistics of PK parameters, all NR and NC values in a data series will be set to missing.

The AUC values will be set to NC if they have been calculated using fewer than three concentrations, and/or three concentrations if the last is C_{max}.

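### Is pamiparib renal clearance unreliable because its AUC interval is unnamed and a lost urine collection has no rule?

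*SAP*

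**What the plan says.** SAP section 10.3.1 defines CL_R as Cum A_eu divided by AUC. A_eu is urine concentration times sample weight, and Cum A_eu adds the "values for each collection interval over the entire collection period". The percentage of dose "will be calculated for each urine collection interval" and is then summed in the same way. For the denominator, the only guidance is that AUC0-∞ "may be used, if appropriate (pamiparib only". The same section also provides AUC0-t, AUC0-9 and AUC0-12. The urine parameters are to be calculated only where that is possible.

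Protocol section 2.2.1 lists "Renal clearance (CL_R; pamiparib only", together with the amount and percentage excreted in urine, among the primary PK endpoints.

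On missing data, SAP section 10.1 says "Missing values will not be imputed". Section 10.4.1, on plasma and whole blood concentrations, says "Where there is NR, these will be set to missing". Section 10.4.2 says that for parameter summaries "all NR and NC values in a data series will be set to missing". Protocol section 9.3 leaves "procedures for accounting for missing, unused, or spurious data" to the CSR and/or the SAP. Protocol section 7.1.2 refers urine collection and processing to a separate document, which is not among those reviewed here.

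**The concern.** With constant renal clearance, the amount excreted over any interval equals CL_R times the AUC over that interval. The ratio is therefore right only when numerator and denominator cover the same time, and the SAP does not say that they must.

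Two kinds of error look possible.

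- A lost interval adds nothing to a plain sum while plasma AUC still covers it, so CL_R and Cum %f_eu read low.
- The AUC can end at a different time from the urine. CL_R then reads low if AUC runs on past the urine and high if it stops first.

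These are primary endpoints with 4 planned completers, so one distorted value would show in the summary.

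**Working it through.** The plan prints no figure for CL_R or Cum %f_eu, so there is nothing to reproduce. The released documents give neither a half-life (h) nor an absorption rate (ka). Both are assumed below, in a one-compartment model with constant renal clearance. The urine intervals (0–4, 4–8, 8–12, 12–24 h, then 24-hourly to 144 h) come from Protocol Appendix 4.

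**Formula.** Reported/true CL_R = (AUC over urine actually collected) / (AUC used as denominator). The share of AUC reached by time t is F(t) = 1 − 2^(−t/h) with instantaneous absorption. With first-order absorption and k = ln2/h, it is F(t) = 1 − [ka·e^(−kt) − k·e^(−ka·t)]/(ka − k).

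**1. Lost interval counted as zero, full AUC kept.** For 12–24 h with instantaneous absorption, the shortfall is 2^(−12/h) − 2^(−24/h):

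| Half-life | Instantaneous | ka 1/h | ka 0.5/h |
|---|---|---|---|
| 6 h | 18.8% | 21.2% | 24.3% |
| 12 h | 25.0% | 26.5% | 28.2% |
| 24 h | 20.7% | 21.3% | 22.0% |

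Losing 0–4 h instead gives 6% to 37% over the same assumptions.

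**2. Effect on a summary of four.** If one patient is at 0.8125 or 0.75 of the true value:

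- The geometric mean ratio is 0.8125^(1/4) = 0.949 or 0.75^(1/4) = 0.931, a fall of 5.1% or 6.9%.
- If the other three values are equal, the log-scale SD is half of |ln 0.8125| or |ln 0.75|. That gives a geometric CV of 10.4% or 14.5%.

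**3. Complete urine to 144 h with AUC0-∞.** The error is the share of AUC after 144 h, 2^(−144/h). This is 0.00%, 0.02% and 1.56% at 6, 12 and 24 h. At 48 and 72 h (ka 1.5/h) it is about 13% and 25%.

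**4. Early discharge.** Under Protocol Appendix 4, blood and urine PK sampling then stop together, so AUC0-t covers essentially the same time as the urine. If AUC0-∞ were used with urine ending at 72 h, CL_R would be low by 2^(−72/h) = 0.02%, 1.6% or 12.5% at 6, 12 or 24 h. The discharge criteria limit this:

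- With 90% of the dose recovered and all of it absorbed, at most 10% can remain. At 72 h that means a half-life of at most 72 × ln2/ln10 = 21.7 h. The 12.5% case needs 0.10/0.80, that is, 20% of the dose unabsorbed and recovered.
- With less than 1% of the dose recovered in a 24-hour interval, complete absorption and single-exponential excretion, what remains is below 1%/(2^(24/h) − 1). That is 1.0% at 24 h and less at shorter half-lives.

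**5. AUC shorter than the urine period.** With ka 1.5/h and half-lives of 6 to 72 h, 144 h urine over AUC0-48 gives ratios of 1.00 to 2.04. Over AUC0-12 it gives 1.37 to 7.24. Mismatches of this kind are plain on inspection.

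**6. Matched intervals.** If the AUC segment of any lost interval is dropped as well, the ratio is 1.00 at every assumed half-life. Every AUC needed comes from data already collected. Matching does not restore Cum %f_eu. A sum with a gap is a minimum value, or is not calculated.

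**The case for a change.** The strongest case for a change is that the SAP sets acceptance rules for plasma and none for urine completeness. The plasma rules are an adjusted R² of at least 0.7, at least three quantifiable concentrations, and a 30% extrapolation limit. The 30% limit governs AUC0-∞ summaries and does not name CL_R. Barring imputation does not say whether a partial sum is reported, flagged or set to NC, and a rule first written in the CSR would follow sight of the data. Urine may also be collected at home after Day 7, while blood sampling is then only optional, so the two can end at different times. At half-lives of 48 to 72 h, even complete 144 h urine over AUC0-∞ would be 13% to 25% low.

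It stands that the text is silent on both points, and that Cum %f_eu with a gap needs a decision by the analyst. The rest is weaker.

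- Counting an uncollected interval as zero is in effect imputing zero, which sits badly with SAP section 10.1. A whole-period sum with a hole in it is naturally NC, and section 10.4.2 then sets it to missing.
- A_eu and %f_eu are derived interval by interval, so a gap is visible. SAP section 9 has protocol deviations considered before database lock.
- AUC0-∞ is optional, and only where appropriate. If a long half-life left much of the AUC extrapolated, AUC0-t would match 144 h urine.
- The scheduled intervals to 144 h fall within CRU residence unless a patient leaves early, and entry requires the ability to give regular urine samples.
- The separate collection document may also cover incomplete collections.

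A rule that accepted only gap-free urine would have its own cost in so small a group. It would discard usable later collections and make CL_R NC whenever 0–4 h was lost.

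**Conclusion.** The gap is real but is one of detail, and it calls for no change. With collection as planned, the error is under 2% at assumed half-lives up to 24 h. Early discharge is covered by AUC0-t, and the discharge criteria limit what AUC0-∞ could add. The 19% to 28% errors need a lost 12–24 h collection that is also summed as zero against a full AUC. The documents give no rate of loss, and the SAP's own wording points away from that handling. A pharmacokineticist would use the same interval above and below the line, and would flag a gapped cumulative value or set it to NC.

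The consequences are also limited. All analysis is descriptive. Urinary and fecal recovery of total radioactivity, a primary objective, is calculated by the radioanalysis laboratory and does not depend on CL_R.

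This conclusion rests on the assumed half-lives. At 48 to 72 h the choice of AUC would matter more (13% to 25% with AUC0-∞), and the extrapolated fraction would show it.

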EC₅₀ half-maximal effective concentration

ECG electrocardiogram

eCRF electronic Case Report Form

EOT end-of-treatment

FDG-PET fluorodeoxyglucose-positron emission tomography

 f_{ef} percentage excreted in feces f_{eu} percentage excreted in urine FSH follicle-stimulating hormone

GCP Good Clinical Practice
GFR glomerular filtration rate

hERG human ether-à-go-go related gene

IB Investigator's Brochure

IC₅₀ half-maximal inhibition concentration

ICF Informed Consent Form

ICH International Council for/Conference on Harmonisation ICRP International Commission on Radiological Protection

IMP investigational medicinal productMDRD Modification of Diet in Renal Disease

MDS myelodysplastic syndrome
MRI magnetic resonance imaging
MTD maximum tolerated dose

PAR poly (ADP-ribose)

PARP poly (ADP-ribose) polymerase

PD progressive disease
PI principal investigator
PK pharmacokinetic(s)
PR partial response

QWBA quantitative whole-body autoradiography

QTc(F) QT interval corrected for heart rate using Fridericia's formula

SAE serious adverse event SCLC small cell lung cancer

SD stable disease

SEM standard error of the mean SOP standard operating procedure

12 December 2018 Page 14 of 72

SSBs single-strand DNA breaks

SUSAR suspected unexpected serious adverse reaction

 $t_{1/2}$ apparent terminal elimination half-life TEAE treatment-emergent adverse event

t_{max} time of maximum observed concentration

ULN upper limit of normal

V_Z/F apparent volume of distribution

12 December 2018 Page 15 of 72

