In Part 1, empty, used unit dose containers will undergo radioanalysis to determine the amount of any residual radioactivity remaining after dose administration and will be discarded upon satisfactory completion of the compliance and accountability procedures. Any unused assembled unit doses will be retained until completion of Part 1 of the study before being returned to the Sponsor or disposed of by the study site, per the Sponsor's written instructions or site standard operating procedures (SOPs).

In Part 2, all unused pamiparib will be returned to the study site.

At the completion of the study, all unused supplies will be returned to the Sponsor or disposed of by the study site, per the Sponsor's written instructions or site SOPs.

5.5. **Dose Hold and Modification**

The relationship between AEs and pamiparib will be assessed by the PI (or designee). Dosing of pamiparib in Part 2 can be withheld for up to 28 days consecutively.

Criteria for treatment modifications and suggested guidelines for the management of some toxicity related to pamiparib are summarized below. These general guidelines may be modified at the discretion of the PI based on discussions with the Medical Monitor and the best clinical judgment at that time; any decisions should be documented. Any toxicity related to pamiparib should be managed according to standard medical practice.

12 December 2018 Page 34 of 72 A maximum of 2 dose reductions is allowed before the patient must be permanently withdrawn from study drug. Dose levels for pamiparib are summarized in Table 2. Pamiparib should be dose-modified as outlined in Table 3.

CONFIDENTIAL

Protocol Reference: BGB-290-106

Table 2: Dose Levels for Pamiparib

Dose Level	Pamiparib
1	60 mg orally, twice daily
-1	40 mg orally, twice daily
-2	20 mg orally, twice daily

Pamiparib may be dose-reduced for a maximum of 2 dose reductions.

Table 3: Criteria for Modification of Pamiparib Dosing for Related Adverse Events

Toxicity	Recommended Dose Modification ^a		
Hematologic			
Anemia (hemoglobin, Hgb)			
Grade 2 (Hgb < 10 - 8 g/dL)	First occurrence: continue dosing at current dose level		
	Second and subsequent occurrences: hold pamiparib until resolved to ≤ Grade 1 or baseline		
	• If resolved ≤ 14 days, then maintain dose levels		
	• If resolved > 14 days, then ↓ pamiparib by 1 dose level		
Grade 3 (Hgb < 8 g/dL)	Hold pamiparib until resolved to ≤ Grade 1 or baseline		
	• If resolved ≤ 14 days, then maintain dose levels		

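### The SAP's formula for the percentage of pamiparib dose excreted in urine divides a percentage (feu), not the amount excreted (Aeu), by dose, so it is circular as printed; probably a one-symbol slip

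*SAP*

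**What the plan says.** SAP 10.3.1 sets out the urine excretion parameters for pamiparib in a table and three short statements.

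- Aeu is the "Amount excreted in urine per sampling interval". For each interval it "will be calculated as the product of urine concentration and urine sample weight (assuming a specific gravity of 1 g/mL").
- %feu is the "Percentage of drug or radioactive dose excreted in urine per sampling interval".
- %feu "will be calculated for each urine collection interval (i) according to the following formula": %feu(i) = [feu(i) / dose] × 100.
- Cum %feu is the sum of the interval %feu values over the whole collection period.

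The SAP does not define feu without the percent sign. The protocol does: its List of Abbreviations gives feu as the "percentage excreted in urine", and Protocol 2.2.1 uses the same meaning when it lists feu and cumulative feu, for pamiparib and for total radioactivity, among the primary urine endpoints.

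SAP 10.3.1 also says that the excretion parameters for total radioactivity are calculated and reported by the radioanalysis laboratory and do not appear in the SAP's tables, figures and listings.

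The divisor is written only as dose, with no definition. Protocol 5.4 says that used Part 1 dose containers "will undergo radioanalysis to determine the amount of any residual radioactivity remaining after dose administration"; the SAP does not say whether that measurement enters any calculation.

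**The concern.** To obtain a percentage of dose, an amount must be divided by the dose. The SAP has a symbol for that amount, Aeu, and explains how to compute it immediately before the formula, yet Aeu does not appear in the formula. What appears is feu, which under the protocol's definition is the answer itself.

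At stake is the specification of a named primary endpoint: the share of the dose recovered in urine as unchanged drug. This is the only formula for it in either document, since Protocol 9.3 refers only to standard noncompartmental methods. SAP section 4 says that the SAP supersedes the protocol's statistical text and that, with the table shells, it is the template for the study report. A formula that cannot be executed as printed leaves the programmer, and anyone checking the output, to guess the numerator.

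**Working it through.** The documents state no numerical value of %feu, so there is no figure to reproduce. The check is of algebra, units and scale.

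**Inputs**

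- Dose: 60 mg (SAP 6.1; Protocol 3.1.1).
- Printed formula: %feu(i) = [feu(i) / dose] × 100 (SAP 10.3.1).
- feu: a percentage (Protocol List of Abbreviations; Protocol 2.2.1).
- Aeu: concentration × sample weight, an amount (SAP 10.3.1).
- Interval amounts: not given in the documents. Values from 0.6 to 30 mg are assumed for illustration. The error factors below do not depend on them.

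**Step 1: the same quantity on both sides.** If feu and %feu are the same percentage f, the formula says f = f × 100/60, that is f × (1 − 1.667) = 0. The only solution is f = 0.

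**Step 2: units.** A percentage has no units, so feu/dose is in 1/mg. The result therefore changes with the unit chosen for dose: the multiplier is 100/60 = 1.67 with dose in mg, but 100/60,000 = 0.00167 with dose in µg. A true percentage of dose cannot depend on that choice. Aeu/dose, mg over mg, has no units and gives a percentage when multiplied by 100.

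**Step 3: scale of the error if the printed formula is followed literally.**

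| Assumed Aeu (mg) | Aeu/60 × 100 (%) | Printed formula, feu as a percentage | Printed formula, feu as a fraction |
|---|---|---|---|
| 0.6 | 1.0 | 1.67 | 0.0167 |
| 1.2 | 2.0 | 3.33 | 0.0333 |
| 6 | 10.0 | 16.67 | 0.167 |
| 12 | 20.0 | 33.33 | 0.333 |
| 30 | 50.0 | 83.33 | 0.833 |

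Worked row for 6 mg: 6/60 × 100 = 10%; printed formula with a percentage, 10/60 × 100 = 16.67; printed formula with a fraction, 0.1/60 × 100 = 0.167. The ratios to the correct value are 100/60 = 1.67 and 1/60 = 0.0167 in every row.

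**Step 4: the cumulative value.** Summing multiplies through by the same factor. Nine assumed intervals totalling 6 mg give 10% with Aeu in the numerator, 16.67 with feu as a percentage and 0.167 with feu as a fraction. Under the percentage reading, any true cumulative value above 60% would print as more than 100%, since 60 × 100/60 = 100.

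**Step 5: what else uses the formula.** Aeu is concentration × weight. Cum Aeu is the sum of Aeu. CLR is Cum Aeu divided by AUC. None of these contains %feu. For feces, the SAP defines the percentage in words and prints no formula.

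**The case against.** The strongest reply is that nobody would be misled. The sentence carrying the formula introduces it as the percent of the dose excreted, the table defines %feu in the same sense, and the preceding paragraph supplies the amount. To produce the 1.67-fold inflation, an analyst would first need the correct percentage and would then have to divide by dose again; the documents offer no separate route to feu. The SAP itself defines only %feu, so the numerator may be better described as an undefined symbol than as a wrong one. This stands, and it is why the point concerns the specification and does not predict a biased result.

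A second reply is that the symbol may be a text-extraction fault. The label of the %feu row in the adjacent table is visibly garbled, and the whole issue is one letter before a subscript. This stands as a reason to check the source page. Against it, the formula line reads cleanly and Aeu is rendered correctly in the paragraph just above.

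A reader might also infer that the SAP divides by the nominal 60 mg and so understates recovery when drug remains in the container. The documents do not support that. The SAP says only dose and never calls it nominal. The protocol places the container measurement under accountability, the text of its product description section (5.1) is not available, and no residue size is given, so no magnitude can be attached. What is left is a missing definition.

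**Conclusion.** As printed, the SAP's formula for %feu of pamiparib is circular and has the wrong units, and Cum %feu inherits the fault. Taken literally, it is 1.67-fold too high with feu as a percentage, or 60-fold too low with feu as a fraction. These factors assume a dose of 60 mg expressed in mg, and nothing else.

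A reader might conclude that the study's urinary or mass-balance results as a whole are wrong. They are not shown to be: the fault is confined to two parameters for unchanged drug in urine, and total-radioactivity excretion is calculated outside the SAP's outputs by the radioanalysis laboratory. Since the intended calculation is clear from the words around it, the likeliest explanation is a notation slip, and numerical harm is possible but not likely. It still merits correction, because this is the only formula given for a named primary endpoint. The undefined dose is a secondary gap in detail.

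**What to change.** Check the symbol against the source page of SAP 10.3.1. If it reads feu(i) there, replace the line with:

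%feu(i) = [Aeu(i) / dose] × 100, with Aeu(i) and dose in the same units.

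The units clause matters because the SAP takes concentration units as the laboratory supplies them. Cum %feu then equals Cum Aeu / dose × 100, which gives a simple programming check.

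As an optional addition, define dose in one sentence, saying whether the residue measured under Protocol 5.4 is subtracted.

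The cost is one or two lines of SAP wording before database lock. No new data are needed, and no other parameter changes as a result of the formula correction.
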